4.2 Analysis Methods

4.2.1 Screening and demographic measurements (Parts A & B, and Part C)

Disposition of patients

For Parts A & B a summary table will be presented specifying the number of patients enrolled, randomised, who received treatment, who completed study, and who terminated prematurely. Data will be summarised by treatment sequence and across all patients (Part A) and olaparib 300 mg bd (Part B).

For Part C a summary table will be presented specifying the number of patients who received treatment, who completed study and who terminated prematurely. Data will be summarised across all patients.

In addition, the number of patients included in each analysis set (Parts A & B only) as well as important protocol deviations will also be summarised within separate tables. Data will be summarised by treatment sequence for Part A and across all patients (Part A) and olaparib 300 mg bd (Part B), and across all patients for Part C.

Demographic data

Descriptive statistics will be presented for age. In addition, frequencies and percentage of patients will be tabulated for the categorical variables age group, sex, race and ethnic group in the same table. Data will be summarised by treatment sequence and across all patients (Part A) and olaparib 300 mg bd (Part B), and across all patients for Part C.

Concomitant medication

Concomitant medications will be summarised by the coded terms in separate tables according to whether the medication is allowed or disallowed. The number of patients receiving a medication will be summarised by treatment for Part A and across all patients for Parts A & B, and separately across all patients for Part C of the study. A medication taken during the course of the study is considered concomitant. A patient is only counted once if receiving the

medication more than once. For detailed information regarding concomitant treatments see Sections 5.6.1 and 5.6.2 of the protocol.

Other baseline data

Other demographic and baseline data, including past treatments and surgery, will be listed and summarised by treatment sequence and across all patients for Parts A & B, and across all patients for Part C.

Treatment Compliance (Part C only)

Study site pharmacy staff will make tablet counts at regular intervals during treatment. Compliance will be assessed by the tablet count and the information will be recorded in the appropriate section of the case record form (CRF). Dates of missed or held doses will be recorded on the CRF.

Estimated compliance is derived from the actual administration days divided by the total planned administration days (last dose date - first dose date + 1), (accounting for dose interruptions).

4.2.2 Pharmacokinetic parameters (Parts A & B)

All PK data received will be presented in data listings, and summaries will be presented for patients in the PK analysis set. Data from patients excluded from the PK analysis set will be included in the data listings, but not in the summaries. Extra measurements (such as unscheduled or repeat assessments) will also not be included in summary tables, but will be included in patient listings. Presentations will be by treatment as defined previously.

In addition, the plasma concentration data and the PK data will be explored graphically. The following plots will be presented:

- Individual plots of olaparib concentration versus time. Time on x-axis with linear scale, concentration on y-axis with *log scale*. There will be one plot per patient showing 3 profiles, one for each treatment (ie, one for fed state, one for fasted state, and one for olaparib 300 mg bd).
- Individual plots of olaparib concentration versus time. Time on x-axis with linear scale, concentration on y-axis with *linear scale*. There will be one plot per patient showing 3 profiles, one for each treatment (ie, one for fed state, one for fasted state, and one for olaparib 300 mg bd).
- Geometric mean (\pm geometric SD, if appropriate) of olaparib plasma concentration versus time. The geometric mean for each treatment (ie, fed state, fasted state, and olaparib 300 mg bd) to be shown in different symbols. Time on x-axis with linear scale and concentration on y-axis with *log scale*. Repeat and include Fed (A) and Fasted (A) only.

- Geometric mean (\pm geometric SD, if appropriate) of olaparib plasma concentration versus time. The geometric mean for each treatment (ie, fed state, fasted state, and olaparib 300 mg bd) to be shown in different symbols. Time on x-axis with linear scale and concentration on y-axis with *linear scale*. Repeat and include Fed (A) and Fasted (A) only.
- Individual plots of olaparib concentration versus time. Time on x-axis with linear scale, concentration on y-axis with *log scale*. All patient profiles for fed state on one plot, repeat for fasted state with patient profiles on one plot. Part A data only.
- Scatter plot of AUC, AUC_{0-t} and C_{max} on separate plots presenting ratio of fed : fasted with patient number denoted on x-axis.
- Geometric mean and 90% CI for the ratio of fed : fasted, plotted separately for AUC, AUC_{0-t} and C_{max}

4.2.3 Food effect analysis (Part A only)

Following log-transformation using natural logarithms, C_{max} , AUC and AUC_{0-t} will be analysed using a mixed effect analysis of variance (ANOVA) model, fitting terms for sequence, patient within sequence, period and treatment (where treatment represents food condition i.e. fed or fasted). Patient within sequence will be treated as a random effect in the model.

Point estimates and adjusted 90% CIs for the difference between treatments, for C_{max} , AUC and AUC_{0-t} , will be constructed based on the following treatment comparisons:

- Fed compared to Fasted

Each confidence interval will be based on the t distribution. The sum of squares of the residuals in the linear model will be used to estimate the variance, which is assumed to be equal for both treatments.

The point estimate and adjusted 90% CIs will then be exponentially back transformed to provide point and confidence interval (CI) estimates for the ratio of interest. No food effect on the PK of olaparib will be concluded if the 2-sided 90% CIs for the ratios of AUC (or AUC_{0-t} as previously noted) and C_{max} are within the range of 0.80 to 1.25.

The analysis will be performed using SAS procedure MIXED in the following manner:

```
PROC MIXED DATA=;
```

```
CLASS patient sequence period treatment;
```

```
MODEL logY=sequence period treatment;
```

```
RANDOM patient(sequence);
```

ESTIMATE 'Fed vs. Fasted' treatment -1 1 / CL ALPHA=0.10;

RUN;

QUIT;

Where logY is log(AUC), log(C_{\max}) and log(AUC_{0-t}) and treatment is coded as 0 = "Fed" and 1 = "Fasted".

Assumptions of normality and constancy of variance will be explored in all analyses and, if necessary, an appropriate transformation (eg, rank) or non-parametric technique (eg, Mann-Whitney test) will be used to validate the results of the main analysis.

Results of this analysis will be presented in an overview table. The original SAS output of this PROC MIXED will be presented in an additional appendix.

An analysis of t_{\max} using the Wilcoxon Signed Rank Test, and the Lehmann median estimator of difference and 90% CIs will also be presented for the following treatment comparisons:

- Fed compared to Fasted

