1.3 Number of patients

The study has been sized to provide an estimate of the difference between olaparib PK parameters in the fed and fasted states. Based on the estimate of within-patient standard deviation (SD) for log AUC from Studies D0180C00002 and D0180C00003 of 0.26, and assuming a true food effect difference of 5%, 42 evaluable volunteers (21 per-sequence) will

give 90% power of showing that the 90% confidence interval (CI) for the food effect (ratio of geometric least-squares means of AUC or C_{max} in the fed state to the fasted state) lies entirely within the range of 0.8 to 1.25.

A total of 48 patients will be entered to ensure that 42 evaluable patients complete the study. nQuery v7.2 was used for the sample size calculations.

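### The prescribed SAS contrast estimates fasted minus fed under a fed-versus-fasted label, so the primary food-effect ratios and intervals come out inverted

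*SAP*

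**What the plan says.** SAP section 4.2.3 specifies a mixed model on the log scale for AUC, AUC0-t and Cmax and gives the PROC MIXED code. Three lines of that section fix the sign of the estimate:

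- Treatment is a classification variable: "CLASS patient sequence period treatment".
- The coding is given beneath the code: "treatment is coded as 0 = 'Fed' and 1 = 'Fasted".
- The contrast is "ESTIMATE 'Fed vs. Fasted' treatment -1 1 / CL ALPHA=0.10".

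The code shows no FORMAT statement and no ORDER= option. The estimate and its limits "will then be exponentially back transformed to provide point and confidence interval (CI) estimates for the ratio of interest".

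The intended direction is stated consistently:

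- Section 4.2.3 names the comparison as "Fed compared to Fasted".
- Section 1.3 defines the food effect as the ratio of geometric least-squares means "in the fed state to the fasted state) lies entirely within the range of 0.8 to 1.25".
- Section 4.2.2 plans a figure described as "Geometric mean and 90% CI for the ratio of fed : fasted, plotted separately for AUC, AUC_{0-t} and C_{max", and a scatter plot of each patient's ratio in the same direction.

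**The concern.** Every verbal description asks for fed over fasted; the code, read with its own coding, delivers fasted over fed. The effect of food on olaparib pharmacokinetics is the sole primary objective (section 1.1), and the same code serves all three log-transformed parameters. A programmer who follows the SAP to the letter would therefore put reciprocal ratios in the overview table and in the model-based interval plot, under a label that says otherwise. Exposure raised by food would be reported as lowered, and the reverse. The model-based plot would also contradict the patient-level fed:fasted scatter plots.

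The SAS output that section 4.2.3 sends to an appendix would carry the same wrong label, so the label there would not help a reader spot the reversal.

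**Working it through.** **Inputs from the SAP.** Coding 0 = Fed, 1 = Fasted; coefficients −1 and 1; exponential back-transformation; 90% interval; limits 0.80 to 1.25 (all section 4.2.3). Within-patient SD of log AUC 0.26; true difference 5%; 42 evaluable patients; 90% power (section 1.3).

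**Step 1: reproduce the plan's own figure.** For a 2×2 crossover on the log scale, SE = 0.26 × √(2/42) = 0.0567, with 42 − 2 = 40 degrees of freedom. Exact power for two one-sided 5% tests against 0.80 and 1.25 is 0.914 at a true ratio of 1.05 and 0.908 at 0.95. The stated 90% is reproduced, and these inputs can be used below.

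**Step 2: sign of the contrast.** The numeric codes sort 0 then 1, so the first coefficient applies to Fed and the second to Fasted:

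(−1) × μ(Fed) + (1) × μ(Fasted) = μ(Fasted) − μ(Fed)

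exp[μ(Fasted) − μ(Fed)] = fasted/fed = 1 ÷ (fed/fasted)

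If the correct interval is (L, U), the code returns (1/U, 1/L).

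**Step 3: numerical confirmation.** One 42-patient crossover was simulated with the SAP's coding, a true fed/fasted ratio of 1.05 and a within-patient SD of 0.26. The fit used fixed patient effects, which give the same treatment contrast as random ones in complete balanced data.

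| Contrast | Ratio | 90% CI |
|---|---|---|
| `-1 1` (as written) | 0.982 | 0.902 to 1.069 |
| `1 -1` | 1.018 | 0.936 to 1.109 |

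The two rows are reciprocals with the limits swapped.

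**Step 4: size at the planned precision.** With t(0.95, 40) = 1.684, the half-width on the log scale is 1.684 × 0.0567 = 0.0955, a factor of 1.100 on the ratio scale.

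| True fed/fasted | Intended result | Result from the code as written |
|---|---|---|
| 1.05 | 1.05 (0.954 to 1.155) | 0.952 (0.866 to 1.048) |
| 1.20 | 1.20 (1.091 to 1.320) | 0.833 (0.757 to 0.917) |

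For point estimates alone, 1/1.30 = 0.77, so a 30% increase appears as a 23% decrease; and 1/0.79 = 1.27, so a 21% decrease appears as a 27% increase.

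**Step 5: effect on the decision rule.** ln 0.80 = −0.2231 and ln 1.25 = +0.2231. The limits are symmetric about zero on the log scale, so an interval lies inside them exactly when its reciprocal does. In the second row of the table, the intended interval crosses 1.25 and the inverted one crosses 0.80: both fail.

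**The case against.** There are three fair points on the other side.

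**The sign depends on level order.** PROC MIXED sorts class levels by formatted value by default. If a text format were attached to treatment, Fasted would sort before Fed and `-1 1` would give the intended fed minus fasted. This is plausible: section 4.2.3 gives word labels with the codes, and section 4.1 requires named treatments in all summaries and listings. But the SAP states numeric coding and shows no format. The point that stands is that the sign of the primary estimate would then hang on a setting the plan does not state. It also means that changing the contrast to `1 -1` alone would introduce the error if a format were in use.

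**The formal conclusion is safe.** The rule beginning "No food effect on the PK of olaparib will be concluded if the 2-sided 90% CIs for the ratios of AUC" gives the same answer either way, and sample size and power do not move. The analysis of tmax is a separate signed-rank procedure and is untouched. All of this is correct. It limits the damage to the direction and size of the reported effect, which matter most when the interval falls outside the limits.

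**Other outputs could expose the reversal.** Geometric means by treatment, the concentration profiles and the patient-level ratio plots are all planned, and the SAS output would normally list the class-level order. An attentive reader may notice a clash. However, the SAP requires no such reconciliation, and the possibility of detection does not make the prescribed code right.

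**Conclusion.** The SAP is wrong as written. With the stated coding, the prescribed contrast estimates fasted minus fed, and the back-transformed ratios and 90% intervals for AUC, AUC0-t and Cmax are the reciprocals of those the text requires. This should be corrected before the analysis is run, because it reverses the direction of the primary estimate.

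The conclusion rests on one assumption: that the class levels sort by their numeric codes, as the SAP's coding implies. The illustrations in the table of intended and inverted results also assume 42 complete patients and the planning SD of 0.26; the inversion itself depends on neither.

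**What to change.** Make one of these two changes in section 4.2.3:

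- Keep 0 = Fed and 1 = Fasted, change the statement to `ESTIMATE 'Fed vs. Fasted' treatment 1 -1 / CL ALPHA=0.10;`, and fix the level order explicitly, for example with `ORDER=INTERNAL` on the PROC MIXED statement.
- Recode 0 = Fasted and 1 = Fed and keep `-1 1`. Numeric and alphabetical order then agree, so the sign is right with or without a text format. This is the more robust choice.

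With either change, request the least-squares means by treatment and add a programmed check that the exponentiated estimate equals the fed geometric least-squares mean divided by the fasted one.

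The cost is one line of code and a short check. The model, the sample size and the decision rule stay as they are.

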4.2.4 Pharmacodynamic parameters (Parts A & B)

All data received will be presented in data listings. Pharmacodynamic summaries will be presented for patients in the QT analysis set by treatment and study day for Part A, and study day for Part B. Data from patients excluded from the QT analysis set will be included in the data listings, but not in the summaries. Extra measurements (such as unscheduled or repeat assessments) will not be included in summary tables, but will be included in patient listings.

The PD variables (absolute values and change from baseline (pre-dose)) will be listed and summarised using descriptive statistics (n, mean, SD, median, minimum, and maximum). Change from baseline (time-matched day -1) in PD variables will also be listed. The QT/QTc outliers are defined as QT/QTc values following dosing that are greater than 450 ms or are increases from baseline (pre-dose) greater than 30 ms. QT/QTc outliers will be highlighted in the data listings and summarised using the following categories:

- values that are
 - >450 ms
 - >480 ms
 - >500 ms

and

- Values that are increases from baseline (pre-dose) of

- >30 ms
- >60 ms
- >90 ms

Box-plots of QTcB, QTcF and QTcI will be presented for absolute values and change from baseline (pre-dose), separately for Part A and Part B.

Patient profile plots of RR, HR, PR, QRS, QT, QTcB, QTcF and QTcI will be presented for absolute values and change from baseline (both pre-dose and time-matched day -1), separately for Part A and Part B.

The number and percentage of patients who meet the ECG outlier criteria at any assessment after start of investigational product (IP) will be tabulated by treatment for Part A (“Fed (A)” and “Fasted (A)”), and by study day for Part B (“Day -1 (B)” and “Day 5 (B)”).

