1. STUDY DETAILS

1.1 Study objectives

Primary objective

- To investigate the effect of food on the pharmacokinetics (PK) of olaparib following oral dosing of the tablet formulation in patients with advanced solid tumours.

Secondary objectives

- To investigate the effect of olaparib on the QT interval corrected for heart rate (QTc) following single (Part A) and multiple (Part B) oral dosing of the tablet formulation in patients with advanced solid tumours.
- To assess the safety and tolerability of olaparib following oral dosing of the tablet formulation in patients with advanced solid tumours.

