1.2 Study design

This is a 3-part study in patients with advanced solid tumours:

- Part A will determine the effect of food on the PK of olaparib and the effect of olaparib on the QT interval following a single oral dose of olaparib tablets;
- Part B will determine the effect of olaparib on the QT interval following multiple oral dosing of olaparib tablets;
- Part C will allow patients continued access to olaparib tablets after the PK and QT phases (Parts A & B) and will provide for additional safety data collection.

A total of 48 patients are planned to be enrolled at approximately 8 sites in Western Europe; approximately 42 evaluable patients will be expected to complete the study.

Part A of this study is a randomised, open-label, 2-treatment period crossover study in approximately 48 patients with advanced solid tumours. Each patient will receive a single oral dose of olaparib tablets 300 mg in each of 2 treatment periods (once in the overnight fasted state and once immediately following a high-fat meal at breakfast time), with at least 5 and no more than 14 days (washout) between doses. Digital ECG (dECG), PK assessments, and safety assessments will be obtained for up to 72 hours post-dose in each treatment period. Additionally, during the first treatment period, patients will undergo baseline dECG assessments on Day -1 (ie, the day prior to dosing) at clock times matched to planned/scheduled dECG assessment times on the dosing day (Day 1). Patients will check into the clinic on the evening of Day -2 (first treatment period) or the evening of Day -1 (second treatment period) and remain resident until 24 hours after each dose of olaparib tablets (Day 2). The dECGs performed on Day 1 in each treatment period will be clock-

matched to the actual times that the Day -1 dECGs are performed in the first treatment period. Patients will return to the clinic for assessments on Days 3 and 4 of each treatment period. On Day 1 of Part A patients should be fasted over the same time period as Day -1.

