Part B of this study is an open-label study in the same patients who participated in Part A. Upon completion of Part A, following a washout period (of at least 5 days and no more than 14 days between the last dose in Part A and Day -1 of Part B) and providing the patient continues to meet the study entry criteria, each patient will receive olaparib tablets 300 mg bd for 5 days. Patients will check into the clinic on the evening of Day -2. On Day -1, baseline dECG assessments will be performed at clock times matched to planned/scheduled dECG assessment times on Day 5. Patients will be discharged from the clinic on the evening of Day -1. Patients will self-administer their olaparib doses under fasted conditions (from 1 hour prior to 2 hours after the olaparib dose) from Day 1 up to the morning of Day 4 on an outpatient basis. On the evening of Day 4, patients will check back into the clinic, and will receive their Day 4 evening dose. On the morning of Day 5, patients will receive their Day 5 morning dose after an overnight fast and will remain fasting for 4 hours post-dose. Patients will undergo dECG and PK assessments pre-dose and for 12 hours post-dose. The dECGs performed on Day 5 will be clock-matched to the actual times that the Day -1 dECGs are performed. Patients will be discharged from the clinic after completing 12-hour assessments on Day 5, and will self-administer their evening Day 5 dose of olaparib tablets. On Day 5 of Part B patients should be fasted over the same time period as Day -1.

On completion of Part B, patients may be entered into Part C and continue to take olaparib tablets (300 mg bd) if they and the investigator agree that this is appropriate. Patients should start Part C immediately after the last dose received in Part B. Patients will have weekly clinic visits for the first 4 weeks; thereafter visits will be every 4 weeks. Part C will be of 12 months' duration from the date the last patient enters this part of the study.

During and after Part C, patients may continue to take olaparib tablets. After the end of Part C patients will be seen as per their normal routine clinical schedule and no clinical data will be collected, other than serious adverse events (SAEs) and drug dispensing/accountability.

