2. ANALYSIS SETS

2.1 Definition of analysis sets

There will be 3 analysis sets considered in this study:

- The safety analysis set will include all patients who receive at least one dose of olaparib.
- The PK analysis set will include all patients who receive an olaparib dose and provide evaluable PK profiles in at least 1 treatment period i.e. fed (A) or fasted (A).

If a patient has a major protocol deviation that affects the evaluability of the PK profile in any treatment period, then the patient will not form part of the PK analysis for that treatment period.

- The QT analysis set will include all patients who have at least 1 evaluable time-matched QT/QTc interval value at a scheduled time point, time-matched between Day -1(baseline) and Day 1(treatment periods 1 or 2) for Part A, or time matched between Day -1(baseline) and Day 5 for Part B.

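### The time-matched Day -1 change in QTc is derived but never summarised, so the QT objective rests on same-day pre-dose changes and has no confidence interval

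*SAP*

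**What the plan says.** Section 1.1 lists as a secondary objective "To investigate the effect of olaparib on the QT interval corrected for heart rate (QTc) following single (Part A) and multiple (Part B) oral dosing".

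Section 1.2 builds the ECG schedule around a drug-free day. In Part A, "during the first treatment period, patients will undergo baseline dECG assessments on Day -1", and the Day 1 recordings of both periods are matched to its clock times. In Part B, "The dECGs performed on Day 5 will be clock-matched to the actual times that the Day -1 dECGs are performed".

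Section 2.1 admits a patient to the QT analysis set on the strength of "at least 1 evaluable time-matched QT/QTc interval value at a scheduled time point".

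Section 3 defines two baselines for the ECG variables. One is the pre-dose value of the same day, a definition that also covers Day -1. The other is the time-matched Day -1 value, and the per-patient change from it is formally derived.

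Section 4.2.4 then treats the two differently:

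- Pre-dose change: "The PD variables (absolute values and change from baseline (pre-dose)) will be listed and summarised using descriptive statistics". The box-plots and the >30, >60 and >90 ms increase categories also use the pre-dose baseline.
- Time-matched change: "Change from baseline (time-matched day -1) in PD variables will also be listed". Its only other appearance is in the patient profile plots.

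No QT or QTc measure is given a model or a confidence interval. The food effect in section 4.2.3 has both.

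**The concern.** The study records a drug-free series in each Part and defines its QT population by time-matched values. It then reports at group level only measures that do not use the matching. There is no placebo arm, so Day -1 is the only drug-free reference over the course of the day.

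Section 4.1 says the sponsor expects regulatory questions on QT and may analyse the available Part A and B data to answer them. Under section 4.2.4 as written, the answer would be descriptive pre-dose changes without an interval. In Part B those changes are measured from a value taken while the patient is already on drug.

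**Working it through.** **1. How the two changes are related.** For one patient, let D(t) be QTc on the dosing day at scheduled time t and B(t) the QTc at the matched clock time on Day -1. Time 0 is pre-dose.

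- Time-matched change: D(t) − B(t)
- Pre-dose change: D(t) − D(0)

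Adding and subtracting B(t) and B(0) gives

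D(t) − D(0) = [D(t) − B(t)] + [B(t) − B(0)] − [D(0) − B(0)].

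So the pre-dose change is the time-matched change, plus the drug-free within-day drift, minus the shift in the pre-dose value since Day -1.

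**2. Part A.** D(0) precedes any olaparib in period 1 and follows a washout of 5 to 14 days in period 2. The last term should therefore be mainly day-to-day variation. The drift term B(t) − B(0) remains in the pre-dose change.

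**3. Part B.** Dosing is twice daily from Day 1, with the last dose before the Day 5 recordings given on the evening of Day 4 (section 1.2). D(0) on Day 5 is therefore an on-treatment trough, and D(0) − B(0) contains whatever QTc effect exists at trough. The pre-dose change subtracts that effect. An effect constant over the dosing interval would cancel completely. The >30, >60 and >90 ms categories inherit the problem. The absolute categories (>450, >480 and >500 ms) do not.

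**4. What the planned tables allow a reader to recover.**

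- Pre-dose change is also defined on Day -1, and summaries are by study day, so the mean of B(t) − B(0) may appear beside the dosing-day change. Subtracting it removes drift. In Part B the result is still reduced by the trough effect.
- The difference in absolute means, mean D(t) − mean B(t), equals the mean time-matched change if the tables are by time point and the same patients contribute.
- The SD of the paired difference cannot be recovered, because it needs the within-patient correlation r. With a common absolute SD s, SD(difference) = s × √(2(1 − r)). For an assumed s = 20 ms and n = 42:
  - r = 0.5: SD = 20.0 ms, 90% half-width 5.2 ms
  - r = 0.9: SD = 8.94 ms, 90% half-width 2.3 ms

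**5. Precision available from the planned data.** The SAP states no QT sizing and no SD for QTc change, so there is no QT figure to reproduce. The n of 42 is the evaluable number in section 1.3, which was set for the food effect. That sizing does reproduce: for two one-sided tests with a within-patient SD of 0.26, power is 0.914 at a true ratio of 1.05 and 0.908 at 0.95, against the stated 90%.

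Half-width of a two-sided 90% interval for a mean paired change = t(0.95, 41) × SD/√42, with SD assumed:

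| Assumed SD (ms) | 90% half-width (ms) |
|---|---|
| 6 | 1.6 |
| 8 | 2.1 |
| 10 | 2.6 |
| 12 | 3.1 |
| 15 | 3.9 |
| 20 | 5.2 |

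**The case against.** A reader might infer that the QT objective gets no estimate at all, or that Parts A and B cannot support any statement on QTc. The SAP does not bear this out. Means and SDs of absolute values and of pre-dose change are planned, and n with SD gives an interval for the pre-dose change directly. Drift on Day -1 may be visible in the same tables. What is missing is a summary of the paired time-matched contrast, and an interval for any QT measure.

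A reader might also assume a drift of several milliseconds and call it as large as the effects of interest. The SAP gives neither a drift nor a QT threshold, so the bias in Part A cannot be sized from it.

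The time-matched baseline has limits of its own, and this part of the objection stands. Part A has one Day -1, in period 1, serving both food conditions. Section 1.2 asks for fasting on Day 1 over the same period as on Day -1, and a single day can match the meal state of at most one condition. The time-matched change for Fed (A) may therefore still carry a meal effect. In period 2 the baseline comes from before the period 1 dose and the washout, so between-day variation enters. The same-day pre-dose value avoids that, which is a reason to keep it as supportive.

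The QT objective is secondary and exploratory in wording, and descriptive reporting is permissible. That does not explain why the measure chosen for description is the one that does not use the matched design.

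Finally, section 4.1 announces a pooled ECG analysis with PK/PD modelling, described elsewhere. Whether it would serve this objective cannot be judged from the SAP. It is called additional, and this SAP contains no such estimate.

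**Conclusion.** The point holds as an omission in section 4.2.4. The time-matched change is collected for, derived and used to define the QT analysis set, but it receives no group summary, and no QT measure receives a confidence interval.

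The consequence is clearest in Part B. The Day 5 pre-dose value is an on-treatment trough, so the summarised change and the increase categories can understate a sustained effect. This follows from the dosing schedule and needs no assumed figure; its size is whatever QTc effect is present at trough, which is unknown. In Part A the pre-dose change retains within-day drift, also of unknown size, which Day -1 summaries may display but which no planned contrast removes.

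The half-widths of about 2.1 to 3.1 ms are illustrative. They rest on 42 patients contributing at a time point and an assumed SD of 8 to 12 ms. The change should be made before the data are seen, but it does not threaten the primary food-effect analysis.

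**What to change.** In section 4.2.4:

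1. Summarise the time-matched change from Day -1 by scheduled time point for Fasted (A), Fed (A) and Day 5 (B), with n, mean, SD and a two-sided 90% CI. A paired t interval per time point is enough. If a model is preferred, use repeated measures with time point as a fixed effect and patient as a random effect, adding treatment and period for Part A.
2. For Part B, also tabulate the >30, >60 and >90 ms increases against the drug-free Day -1 baseline.
3. Name one QTc correction as the main one before the data are seen. Section 3 plans three and allows more, with none in the lead.
4. Keep the pre-dose change as supportive.
5. State that the Fed (A) time-matched change may still carry a meal effect, and that period 2 of Part A uses a baseline recorded in period 1.

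The cost is a few extra tables and at most one model. No new data, visits or recordings are needed.
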